3.2 Secondary Objectives

The **exploratory, hypothesis generating aims** are to (2) describe relationships between neural markers and (a) cognitive function and (b) affect during MBSR; and (3) explore the moderating effect of inter-individual differences in the expression of genes involved in stress responses on neural markers of changes in cognitive function during MBSR.

4 Study Design and Endpoints

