4.2.3 Exploratory Endpoints

Exploratory endpoints will include correlations between neural markers of changes in cognitive function (or baseline neural markers if no changes are found) and changes in (a) cognitive function from before to

CONFIDENTIAL

three months after MBSR versus HEP and (b) self-reported affect from before to within three weeks after and three months (+/- three weeks) after the intervention. Exploratory endpoints will also include the moderating effect of inter-individual differences in the expression of genes involved in stress responses on neural markers of changes in cognitive function. Exploratory endpoints were chosen to gain preliminary evidence of relationships between neural markers and objectively and subjectively measured cognitive and affective phenotypes, as well as to gain preliminary evidence for underlying biological mechanisms (i.e., gene expression). See Figure 1 for a graphical representation of these relationships.

5 Study Enrollment and Withdrawal

The R00 study will enroll up to 32 evaluable participants (i.e., 16 per group) for the pilot randomized controlled trial. Up to 40 participants will be enrolled to obtain this final sample size.

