10.2 Statistical Hypotheses

The sample size is too small to make inferences about relationships evaluated in the R00 study to the larger population of postmenopausal women with breast cancer. For the primary aim, effect sizes for neural markers of changes in cognitive function will be obtained. For the exploratory aims, effect sizes for correlations of exploratory outcomes to neural markers of changes in cognitive function will be calculated. The effect sizes for these relationships will be determined in the R00 study, which will inform the sample size for a well-powered study planned for future R01 applications.

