10.5 Sample Size

The R00 study will recruit up to 32 participants (i.e. 16 participants per group) with analyzable data. Up to 40 participants will be recruited to reach this goal. The projected sample size is sufficient to meet the specific aims of the R00 study and falls within the range of pilot neuroimaging studies.^{53,54} It is unknown what effect sizes for the intervention versus active control will be uncovered for neural markers in this population. However, based on the investigators' finding of large effect sizes for neural markers of cognitive changes in the K99 study, group sample sizes of 16 will achieve 78.1% power to reject the null hypothesis of no effect size when the population effect size is 1 and the significance level (alpha) is 0.05 using a two-sided, two-sample equal variance t-test.

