**Aim 1: Evaluate the preliminary efficacy of MBSR to improve neural markers of cognitive changes during AI therapy.** **fMRI:** Data will be preprocessed using Statistical Parametric Mapping-12 (SPM-12; [www.fil.ion.ucl.ac.uk/spm](http://www.fil.ion.ucl.ac.uk/spm)) to normalize images into standard space so that all brains can be compared. Talairach PickAtlas will be used to define regions of interest (ROIs) for cognitive and emotion processing. Neural activation will be evaluated using the blood-oxygen-level-dependent (BOLD) signal. SPM-12 will extract BOLD activation in these ROIs. Brain activation maps will describe (1) between-group differences in brain activation in ROIs for the MBSR versus active control group pre- and post-intervention and (2) within-group change scores in brain activation for each group pre- to post-intervention. **fcMRI:** BOLD signal time series will be extracted from ROIs of the default mode network. Physiological noise and motion artifact regressors will be removed. Residual time series from each ROI will be filtered between 0.01-0.08 Hz. Analyses will be performed with and without a global signal regressor to assess impact on connectivity. Parameter estimates representing connectivity between neural regions will be extracted. Functional connectivity maps will describe between-group differences in connectivity in ROIs pre- and post-intervention and within-group change scores in connectivity pre- to post-intervention. **dMRI:** Data will be analyzed using ExploreDTI ([www.exploredti.com](http://www.exploredti.com)), FreeSurfer ([surfer.nmr.mgh.harvard.edu](http://surfer.nmr.mgh.harvard.edu)), and the diffusion toolbox of the Functional MRI tool of Brain Software Library ([www.fmrib.ox.ac.uk/fsl](http://www.fmrib.ox.ac.uk/fsl)) to perform quality assurance for images, process them for characterization of the integrity of white matter tracts, and match white matter tracts to structural MRI data. White matter tracts between cortical and subcortical ROIs will be evaluated to describe how white matter integrity is affected. Fractional anisotropy (FA) values for white matter tracts will be extracted. FA maps will describe (1) between-group differences in FA in ROIs for the MBSR versus active control group pre- and post-intervention and (2) within-group change scores in FA pre- to post-intervention.

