**Exploratory Aim 2a: Describe relationships between neural markers and changes in cognitive function.** Change scores for neuroimaging parameters obtained in Aim 1 will be correlated with change scores on measures of cognitive function to describe how neural markers are associated with cognitive changes. If no changes in neural markers are found, relationships between baseline neural markers and changes in cognitive function will be described. **Exploratory Aim 2b: Describe relationships between neural markers and changes in affect.** The methods in 2a will be used to describe relationships between neural markers and changes in affect. **Exploratory Aim 3: Explore the moderating effect of inter-individual differences in the expression of genes involved in stress responses on the relationship between AI therapy and neural markers during MBSR.** Differential expression (DE) of genes in relation to fMRI, fcMRI, and dMRI parameter estimates at each time point will be determined using correlational analysis. Expression intensity varies widely over genes and needs to be adjusted between genes to provide a reliable measure of DE. We will adjust the standard errors and estimate the correlation of genes with each outcome. We will adjust for multiple hypothesis testing through estimation of the FDR using the Benjamini-Hochberg procedure. The FDR q-value will be determined empirically.

**Possible Problems and Solutions.** The sample size is too small to make inferences about relationships evaluated in the R00 study to the larger population of postmenopausal women with breast cancer. The effect sizes for these relationships will be determined in the R00 study, which will inform the sample size for a well-powered study planned for future R01 applications (see Plan for Research Independence in the Final Progress Report for the K99 Phase). If no relationships are found between gene expression levels for stress response pathways and neural markers, other pathways will be evaluated (e.g., DNA repair).

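### The undefined no-change condition in Aim 2 may replace the change-change correlations with baseline correlations, and it is not needed

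*SAP*

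**What the plan says.** SAP Exploratory Aim 2a opens without any condition: "Change scores for neuroimaging parameters obtained in Aim 1 will be correlated with change scores on measures of cognitive function". It then adds a fallback: "If no changes in neural markers are found, relationships between baseline neural markers and changes in cognitive function will be described". Aim 2b takes over the same approach for affect: "The methods in 2a will be used to describe relationships between neural markers and changes in affect".

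Protocol 4.2.3 builds the condition into the definition of the exploratory endpoint. After naming correlations with neural markers of change, it inserts in parentheses "or baseline neural markers if no changes are found". The SAP fallback does not say whether it stands in for the main analysis or is added to it; the protocol parenthesis is worded as an alternative.

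On purpose, Protocol 3.2 labels the aim exploratory and hypothesis generating: "describe relationships between neural markers and (a) cognitive function and (b) affect during MBSR". Protocol 10.2 states what it should yield: "effect sizes for correlations of exploratory outcomes to neural markers of changes in cognitive function will be calculated". The same section and the last paragraph of the SAP say that the study's effect sizes will set the sample size of a later, larger study.

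**The concern.** Whether neural change has been found decides which predictor enters the correlation, yet neither document says how that is decided. SAP Aim 1 produces between-group differences before and after the intervention and also, for fMRI, "within-group change scores in brain activation for each group pre- to post-intervention", with parallel outputs for fcMRI and dMRI. Nothing says which of these outputs counts, whether a test or a size threshold applies, or whether the decision is made marker by marker or once for all markers. Two analysts could follow the text faithfully and report different endpoints from the same data.

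The condition also has no statistical basis. A small average change does not mean that individual women did not change, and it is the spread between women that a correlation uses. The replacement answers another question: whether starting level predicts later cognitive change, rather than whether the two changes move together.

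What is at stake is the use of the numbers. If the later study is planned on the change-change effect size, a rule that can supply a different quantity in its place works against the stated purpose of the aim.

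**Working it through.** **Inputs.** From Protocol 10.5: "The R00 study will recruit up to 32 participants (i.e. 16 participants per group) with analyzable data", with effect size 1, two-sided alpha 0.05, an equal-variance two-sample t-test, and stated power of 78.1%. From Protocol 7.1.1: imaging at TP0 and TP1, neuropsychological tests at TP0 and TP2. The documents give no figure for Aim 2 and no criterion for the trigger, so steps 3 to 5 rest on stated assumptions.

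**1. The plan's own figure.** Noncentral t with df = 30 and noncentrality 1 x sqrt(16/2) = 2.83 gives power of 78.14%, against 78.1% stated. It reproduces.

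**2. Does the correlation need a non-zero mean change?** For neural change D and cognitive change C,

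r = sum[(D_i - mean D)(C_i - mean C)] / sqrt( sum(D_i - mean D)^2 x sum(C_i - mean C)^2 ).

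Add any constant m to every D_i. The mean rises by m, each deviation stays the same, and so does r. The only requirement is that D varies between women. If the arms are pooled, a between-arm difference in mean change feeds into r, but its absence does not make r inestimable. This step needs no assumption.

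**3. How often might the trigger fire for one marker?** Assume, for illustration only, that the condition means p >= 0.05, two-sided. For a paired test, noncentrality is d x sqrt(n) with df = n - 1, where d is the mean change in SDs of change. For a between-arm test it is d x sqrt(16/2) with df = 30. For example, d = 0.5 and n = 16 gives noncentrality 0.5 x 4 = 2.0; d = 0.5 and n = 32 gives 0.5 x 5.66 = 2.83. The probability of declaring no change is:

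| True d | Paired, one arm, n = 16 | Paired, pooled, n = 32 | Between arms, 16 per arm |
|---|---|---|---|
| 0.2 | 88% | 80% | 91% |
| 0.3 | 80% | 62% | 87% |
| 0.5 | 54% | 22% | 72% |
| 0.8 | 15% | 0.8% | 41% |
| 1.0 | 4% | 0.02% | 22% |

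The spread across a row shows how much the undefined choice of comparison matters.

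**4. A global trigger.** If the rule applies only when no marker at all shows change, it fires less often. The number of markers is not stated. With an assumed 10 independent markers, each with the same true change and a paired test at n = 16, the probability is 0.797^10 = 0.10 at 0.3 SD and 0.535^10 = 0.002 at 0.5 SD. With perfectly correlated markers it returns to the single-marker 80% and 54%. Real markers lie between.

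**5. How different is the replacement?** Assume equal variances at both scans, test-retest correlation rho, and a baseline linked to cognitive change only through neural change. Then corr(baseline, D) = -sqrt((1 - rho)/2), and corr(baseline, C) = -r x sqrt((1 - rho)/2). With an assumed r = 0.5:

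- rho = 0.3: -0.5 x sqrt(0.35) = -0.30
- rho = 0.5: -0.5 x sqrt(0.25) = -0.25
- rho = 0.7: -0.5 x sqrt(0.15) = -0.19

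A simulation (20,000 runs, N = 32, one marker, paired test, true change 0.3 SD) agrees. About 62% of runs switch. In those runs the change-change r still averages 0.50, while the baseline r averages -0.30 to -0.20. If the baseline r replaces it, the average reported correlation is about 0.00 to 0.06. The sign and the gap belong to these assumptions. That the two correlations are different quantities does not.

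**6. Precision if always reported.** On the Fisher z scale the half-width is 1.96/sqrt(n - 3). For n = 32 it is 1.96/sqrt(29) = 0.36, so an observed r of 0.5 has a 95% interval of 0.18 to 0.72. For n = 16 it is 1.96/sqrt(13) = 0.54, giving 0.01 to 0.80. The estimate is imprecise but available, whatever the mean change.

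**The case against.** A reader might infer three stronger things, and the documents support none of them.

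*That the plan discards the change-change correlations.* The SAP states that analysis without condition, so does the Protocol Summary, and Protocol 10.4.13 refers exploratory analyses to the SAP. The SAP fallback can be read as an addition. Only the parenthesis in Protocol 4.2.3 makes baseline markers an alternative. Replacement is therefore a possible reading, not an established one.

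*That the rule is a significance test on mean change.* Neither document mentions a mean, a test or a threshold for this condition. SAP Aim 1 is descriptive, and the only test tied to sample size is the two-sample t-test in Protocol 10.5. The percentages in the table are illustrations of one possible reading.

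*That the results would be a mixture, with some markers reported by change and others by baseline.* This requires switching marker by marker. The plural wording can equally mean that nothing changed anywhere. On that reading the set is not mixed, and the single-marker rates overstate how often the switch happens.

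It is also fair to say that the fallback is written in advance in both documents, that the aim is exploratory, and that no error rate depends on it. All of this stands, and it limits the harm. It does not remove it: specifying a rule in advance helps little when its trigger is undefined, and effect sizes for planning are exactly what the aim is meant to deliver.

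**Conclusion.** The point holds in a limited form. Three parts rest on the documents and on algebra alone: the trigger is undefined, the change-change correlation does not depend on mean change, and the baseline correlation is a different quantity. That the rule may replace the wanted effect size rests on the Protocol 4.2.3 wording, because the SAP leaves replacement or supplement open.

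The size cannot be fixed from the documents. For a single marker, with a paired test at 0.05 assumed, the condition would be met about 54% (n = 16) or 22% (n = 32) of the time at a true change of 0.5 SD, and 80% or 62% at 0.3 SD. A global trigger would fire less often. The possible reversal of sign depends on an assumed correlation structure and should not be read as a prediction for this trial.

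The primary endpoint and any confirmatory conclusion are untouched. It is worth correcting because it bears on figures intended for the next study's sample size, and the correction is cheap.

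**What to change.** Delete the condition in SAP Exploratory Aim 2a (and so in 2b) and in Protocol 4.2.3. In its place, state that:

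- the correlation of neural change with cognitive change, and with change in affect, is reported with a 95% confidence interval for every marker, whatever Aim 1 shows;
- the correlation of baseline neural markers with those same changes is reported for every marker as a second exploratory set, labelled separately and not offered as a substitute.

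If the sponsor prefers to keep a condition, the SAP should define it (measure of change, comparison, threshold, per marker or overall) and say that the baseline analysis is additional.

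The data are already scheduled, so no visit or measurement is added. The cost is a wording change in two documents, one extra table, and a larger number of exploratory correlations. Since Protocol 10.4.11 generally applies no control for multiple comparisons, the second set should be presented as estimates with intervals rather than as findings.

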5.1 Inclusion Criteria

In order to be eligible to participate in this study, an individual must meet all the following criteria:

1. Willingness and ability to participate in study assessments and the eight-week intervention
2. Female
3. Age 18-79
4. Able to speak and read English
5. Post-menopausal (defined as [A] amenorrhea persisting for an entire year, [B] oophorectomy or ovarian suppression/ablation, or [C] hysterectomy and age greater than 51 years)
6. Diagnosed with stage 0 (i.e., ductal carcinoma in situ [DCIS]) or stage I, II, or III breast cancer
7. Post lumpectomy or mastectomy and any re-excisions
8. Post cytotoxic chemotherapy, if prescribed
9. Taking AI therapy OR scheduled to begin AI therapy by the time of the first follow-up study assessment (i.e., TP1)
10. Written, informed consent

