**Statistical Analysis Plan (SAP) for R00NR015473**  
**August 8, 2017**

**Data analysis.** Data analysis will be performed using SPSS Statistics 24 (IBM Corp., Armonk, NY). Using exploratory and descriptive analyses, we will first evaluate whether any data anomalies (e.g., nonrandom missing data, erroneous outliers, multicollinearity, possible confounding) may invalidate planned analyses and then summarize data in terms of location and variability using appropriate descriptive statistics, given the variable's level of measurement and observed data distribution. As needed, appropriate remedial approaches (e.g., data transformations, imputation, nonparametric analysis methods) will be applied.

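### SAP Aim 3 correlates gene expression with imaging values without adjusting for age or prior chemotherapy, so genes that only track these can appear linked to neural markers

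*SAP*

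**What the plan says.** The SAP's Exploratory Aim 3 gives the whole method in a few sentences. Expression is related to fMRI, fcMRI and dMRI values: "parameter estimates at each time point will be determined using correlational analysis". The adjustment it names concerns precision: "We will adjust the standard errors and estimate the correlation of genes with each outcome". Multiplicity is handled by "estimation of the FDR using the Benjamini-Hochberg procedure", with no fixed q-value. No participant characteristic enters the analysis. Protocol Section 10.4.13 refers exploratory analyses to the SAP, so no other text supplies a covariate.

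The SAP's opening paragraph on data analysis promises a preliminary look for anomalies, among them "nonrandom missing data, erroneous outliers, multicollinearity, possible confounding", after which "appropriate remedial approaches (e.g., data transformations, imputation, nonparametric analysis methods) will be applied" as needed.

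Protocol Section 5.1 admits women aged 18 to 79 who are postmenopausal, with or without earlier chemotherapy ("Post cytotoxic chemotherapy, if prescribed"). Chemotherapy is a randomisation stratum (Sections 4.1 and 10.6.1) and has no stated role in any analysis.

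The two documents differ on the imaging variable. The Protocol Summary associates expression with imaging change scores, whereas the SAP uses values at each time point. Imaging is done only at TP0 and TP1 (Section 7.1.1).

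**The concern.** A correlation across women between expression and an imaging value picks up anything that moves both. Age and prior chemotherapy are plausible candidates. Protocol Section 2.1 itself describes altered brain activation in women treated with chemotherapy, and says the contributions of chemotherapy and anti-estrogen therapy could not be separated.

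Neither safeguard in the plan deals with this. Stratified randomisation balances the arms, but Aim 3 does not compare arms. Benjamini-Hochberg limits chance findings; a confounded correlation is a genuine correlation with the wrong explanation.

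Two uses of the results are exposed. Protocol Section 4.2.3 wants preliminary evidence of biological mechanism from gene expression. Protocol Section 10.2 and the SAP intend the effect sizes to inform the sample size of a later study. Confounding biases the effect size itself, whether or not anyone tests it.

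**Working it through.** **The plan's own figure.** The only power statement (Protocol Section 10.5) is for the two-arm comparison: 16 per group, effect size 1, two-sided 0.05, 78.1%. With 30 degrees of freedom and noncentrality 1 × √(16/2) = 2.83, the exact t-test power is 78.14%, so it reproduces. It says nothing about Aim 3, for which no figure is given. The check below takes n = 32 from the same section.

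**Assumed inputs.** The documents give no correlation of age or chemotherapy with expression or imaging. Assumed for age: 0.3-0.6 with the marker and 0.3-0.5 with expression.

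**Induced correlation.** If expression and marker are unrelated given age, the raw correlation is the product

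r(raw) = r(expression, age) × r(marker, age),

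which runs from 0.3 × 0.3 = 0.09 to 0.5 × 0.6 = 0.30.

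**Nominal rejection at n = 32.** The unadjusted test has 30 degrees of freedom, critical t 2.042 and critical |r| = 2.042/√(2.042² + 30) = 0.349. Simulation with normal variables gives:

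| r(expression, age) | r(marker, age) | r(raw) | P(p<0.05), unadjusted | P(p<0.05), adjusted |
|---|---|---|---|---|
| 0.3 | 0.3 | 0.09 | 8% | about 5% |
| 0.3 | 0.5 | 0.15 | 13% | about 5% |
| 0.4 | 0.6 | 0.24 | 26-27% | about 5% |
| 0.5 | 0.5 | 0.25 | 28-29% | about 5% |
| 0.5 | 0.6 | 0.30 | 39% | about 5% |

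A Fisher-z check agrees at the upper end: atanh(0.30) × √29 = 1.67, and P(Z > 1.96 − 1.67) is about 39%.

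**Chemotherapy.** Assume a 16/16 split and that expression and marker each differ by d standard deviations between women with and without chemotherapy. Then r(raw) = d²/(4 + d²). For d = 0.5, 0.8 and 1.0 this is 0.06, 0.14 and 0.20, with nominal rejection of 6.2%, 11.9% and 19.9%. Adjustment returns it to 5%.

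**After Benjamini-Hochberg.** The SAP fixes neither q nor the number of genes. Assume q = 0.05, 200 genes, 10% of them tracking age and none truly linked. For the five rows above, at least one false link appears in about 6%, 8%, 18%, 20% and 32% of runs, against about 5% when no gene tracks age. With 30% tracking age, the range is about 7% to 58%.

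These are rates per list, so they do not compare directly with the table. Per gene, at (0.5, 0.5) with 20 of 200 genes tracking age, the mean number listed was 0.38. That is at most 0.38/20 = 1.9% of the age-tracking genes, against 28-29% nominally.

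**Consequence for planning.** A spurious r of 0.247, the mean raw correlation in the (0.5, 0.5) row, taken at face value would suggest [(1.96 + 0.84)/atanh(0.247)]² + 3, or about 127 participants at 80% power, to study a link that is absent given age.

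**The case against.** The strongest reply has four parts.

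- **The SAP already looks for confounding.** It does, and its list of remedies is open-ended, so a reader who infers that adjustment is ruled out goes too far. But the examples given ("data transformations, imputation, nonparametric analysis methods") do not remove a confounder, none is named, and any adjustment would be chosen after seeing the data. The provision is vague rather than absent.
- **The Protocol Summary uses change scores.** Change removes stable differences between women in imaging level, so confounding by age would be weaker. This stands as a limit on the size of the problem. It does not settle it, because the SAP states the other version and the two conflict.
- **The age spread is narrower than 18-79.** All women must be postmenopausal. Ovarian suppression or ablation admits some younger women, but the full 61-year span should not be taken as the likely spread. This also stands.
- **Aim 3 is exploratory and disclaims population inference.** True, and it limits the severity. It does not excuse biased effect sizes, because these are what the aim is meant to deliver.

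A reader might also infer that age- or treatment-related genes will be reported, or will make up most of the list. The documents do not support either. All confounder strengths are assumed, the excess is slight at the weak end, and in the Benjamini-Hochberg runs with 10% of genes tracking age most lists were empty across the assumed range.

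**Conclusion.** The gap is real. As written, Aim 3 is an unadjusted correlation across women who differ in age and chemotherapy history, and neither randomisation nor false-discovery control repairs that. Genes that only track these factors can appear linked to neural markers, and the effect sizes passed to the next study can be biased.

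The size depends on the assumed age correlations and on approximate normality: a raw r of about 0.09-0.30 and nominal significance in about 8-39% of cases at n = 32, against 5% with adjustment. Control of the false discovery rate, a narrower age range or change scores would each make the excess smaller.

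It would go beyond the documents to extend this to the baseline-marker fallback in Aim 2, or to say that blood-cell mix must be modelled; neither was computed. This is a worthwhile correction to an exploratory aim, and no primary conclusion depends on it.

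**What to change.** In SAP Exploratory Aim 3, replace the plain correlation with a per-gene linear model, or a partial correlation, with age and the chemotherapy stratum as prespecified covariates. Report it beside the unadjusted correlation so that readers can see how far each association depends on them.

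Reconcile the Protocol Summary (change scores) with the SAP (values at each time point), stating which imaging variable Aim 3 uses.

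The cost is SAP wording and two degrees of freedom. Demographic and clinical data are collected at TP0 (Protocol Section 7.1.1), and randomisation already needs the chemotherapy stratum. Going from 30 to 28 degrees of freedom moves the critical |r| at two-sided 0.05 from 0.349 to 0.361.
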